# Core aspects of therapy conditions

|  |   | Emotion Focused (ST-EF)  | non-emotion focused - Active Control (ST-AC)  |
|--|---|--|---|
| Week 1-2 (diagnostic phase)                   |   |  |   |
| Dose  | Individual sessions                           | 
 
• 2 individual sessions, i.e. weekly sessions of 50 minutes with the individual therapist
 
  |   |
|  | Additionally per week                         | 
 
• Supporting group therapies: ergotherapy (2×60 min), movement therapy (1×60 min)
 
• meetings of group and individual therapists to coordinate the content of treatment
 
  |   |
| Focus   | Diagnostics and case conceptualization        | 
Patients arrive in their groups
 
 
• undergo detailed full diagnostic assessment
 
• get acquainted with individual and group therapist
 
• provide biographical information
 
• recognition of key issues
 
• discussion of diagnostic findings including all relevant questionnaires
 
• generation of individual schema-mode-model
 
 |   |
| Week 3-7 (changing phase)                     |   |  |   |
| Dose  | Individual sessions                           | 
10 sessions (2/week) of 50 minutes with individual therapist; 5 sessions of 50 min (or 10, i.e. 2×25 min/week) with the co-therapist; 5 weekly group sessions of 100 min including max. 10 patients
   |   |
|  | Additionally per week                         | 
Communicative movement therapy (2×60 min), awareness therapy (2×60 min, incl. daily 30 min to practice), music therapy (60 min), time for self-reflection (60 min/day)
  | 
Movement therapy (2×60 min), Yoga or progressive muscle relaxation, PMR (2×60 min); social competence training (2×60 min)
  |
| Focus   | Clarification, "mode awareness", self-empathy | 
 
• Diagnostic imagination of all relevant deprivations or traumas of childhood (as often as possible)
 
   | 
 
• Intensive psychoeducation on schemas, schema coping, modes (child modes, parent modes, coping modes, healthy adult and happy child modes), needs, emotions as well as on normal development of children
 
 |
|  |   | 
 
• Chair dialogs to clarify function and goals of dysfunctional coping modes, to fight dysfunctional parent modes (punitive or demanding) or to comfort the vulnerable child mode
 
   | 
 
• Discussion of self-observation protocols
 
  |
|  |   | 
 
• Limited reparenting if vulnerable child or angry child mode are activated
 
  | 
 
• Generation of mode-specific micro behavioural analysis of situations on the basis of standardized worksheets
 
  |
|  |   | 
 
• Chair dialogs to clarify inner conflicts in daily life situations
 
  |   |
|  |   | 
 
• Imagery rescripting of childhood situations
 
  |   |
| Week 8-9 (becoming one's own therapist phase) |   |  |   |
| Focus   | Development of new self-management strategies | 
 
• Development of new functional strategies on the basis of emotional needs and functional goals
 
  | 
 
• Discussion of more functional strategies, pro/con debates
 
   |
|  |   | 
 
• Imaginary work for practicing in an emotional activated context in the now
 
   |   |
|  |   | 
 
• Role plays within the session
 
  |   |
|  |   | 
 
• BEATE-Steps in order to improve self-management
 
  | 
 
• BEATE-Steps in order to improve self-management
 
   |

Borderline Personality Disorder and Emotion Regulation

Effects of emotion-focused vs. cognitive schema therapy interventions on emotion regulation deficits in borderline personality disorder - associations between clinical efficacy, brain network function and local glutamate/GABA metabolism

Ethiks approval 04.06.2018, last time edited

Statistical Analysis Plan

Data evaluation and analysis

The SPSS software package (IBM Corp. released 2013, IBM SPSS Statistics for Windows, Version 25.0. Armonk, NY, USA) will be used to perform the following statistical tests to address verification (or falsification) of the previously formulated hypotheses.

Cross-sectional analysis of baseline (T0) MRI-data

Separate for rs-fMRI and ¹H-MRS data: A seed-based correlation analysis will be used to explore the whole-brain RSFC pattern of the regions being central to this study, i.e., the aMCC and DLPFC. Analysis of variance (ANOVA) will be applied to test for RSFC differences between patient groups and controls, as well as for group differences of the local Glx and GABA concentrations and the Glx/GABA balance in the aMCC and DLPFC between patients and controls.

Associations between rs-fMRI and ¹H-MRS data: A linear mixed model analysis will be performed to investigate differences of associations between RSFC in SN and ECN networks and Glx or GABA concentrations at the aMCC and DLPFC between patients and controls.

Follow-up (T0-T1, T1-T2, T0-T2) analysis of treatment effects on primary and secondary outcome criteria

Evaluation of changes of core symptoms and their clinical significance: In each therapeutic condition the improvement of each patient in measures of the primary and secondary outcome criteria will be estimated by the Reliable Change Index (RCI) (Wise, 2004)(Jacobson and Truax, 1991), which summarizes changes at the level of an individual in the context of observed changes for the whole sample. The RCI provides information about the functioning of an individual before/after therapy on an outcome measure, including the normative information about this measure (Atkins *et al.*, 2005) by dividing the difference between pre- and post-treatment scores by the standard error (that includes also the reliability coefficient, not only the standard deviation of the measure) (Hurst and Bolton, 2004). The change will be considered as being unlikely the product of measurement error (i.e., considered reliable), if the RCI is greater than 1.96. When the individual has a change score greater than 1.96 it can be assumed that the individual has improved.

Follow-up (T0-T1, T1-T2, T0-T2) analysis of treatment effects on MRI target parameters (RSFC, Glx, GABA) and of potential associations between these neurobiological changes and clinical improvement according to outcome criteria

Separate for rs-fMRI and ¹H-MRS data: Analysis of variance (ANOVA) for repeated measures will be applied to test for effects of group belonging (ST-EF, ST-AC, and healthy subjects; ST-EF vs. ST-AC) on changes of RSFC, Glx and GABA over time, as well as for within-subject changes between T1 and T2 scans.

Associations between RSFC and the local Glx and GABA concentrations: A linear mixed model analysis will be performed to investigate changes after 9 weeks (and 6 month respectively) of either therapeutic condition (ST-EF, ST-AC) compared to unspecific changes over time in healthy controls as well as between treatment groups. In a first step, this analysis will be performed separately in both treatment groups and healthy controls and for both neurotransmitters (Glx, GABA) and both spectroscopic and functional connectivity target regions (aMCC, DLPFC). In the second step, potential treatment condition driven differences in the correlations between metabolic and RSFC parameters will be investigated by applying the same model including the factor treatment group.

Interrelation between clinical outcome parameters and neurobiological findings: A linear mixed model analysis will be used that includes those MRI-data (RSFC, Glx, GABA) that have been significantly affected by therapy (**T0-T1**, **T1-T2**, **T0-T2**) and those clinical scores that reached the highest RCI. The detected significant interactions will be compared between the ST-EF and ST-AC treatment condition.

Data handling

Prior to starting recruitment of the participants, a project specific database will be created, which considers all GCP requirements in terms of user authentication, anonymization of participants, audit log and query management. This database will contain all project related data (demographic data, RSFC, ¹H-MRS and psychopathology data). All clinical ratings will be determined according to the corresponding manuals and will be separately stored for the time points T0, T1 and T2.

MRI data (anatomic and rs-fMRI data) will be acquired in the DICOM-Standard format, ¹H-MRS data are collected in a vendor specific format (.rda and .dat Siemens files). All raw and processed data are stored on a RAID computer system, which is serviced by the MPJ and equipped for standardized data access and management. All data will be available to longitudinal research and joint research with cooperation partners in this field.

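### The baseline patient-control MRI comparison is an ANOVA with no stated covariates or matching, so a group difference could reflect age, sex, head motion or voxel tissue content; the patient grouping for RSFC is also unclear

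*SAP*

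**What the plan says.** The SAP section on cross-sectional analysis of baseline (T0) MRI data covers the group comparison in one sentence. For connectivity it plans an ANOVA for "RSFC differences between patient groups and controls". The sentence then extends the same test to the metabolites, ending with the "Glx/GABA balance in the aMCC and DLPFC between patients and controls". The grouping is thus plural for RSFC and a single patient group for Glx, GABA and their ratio.

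The next paragraph of that section plans a mixed model for the link between RSFC and metabolites, again for patients and controls, and again without covariates: "A linear mixed model analysis will be performed to investigate differences of associations between RSFC in SN and ECN networks".

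The treatment arms are named only later, for the follow-up ANOVA on MRI parameters, which tests "effects of group belonging (ST-EF, ST-AC, and healthy subjects; ST-EF vs. ST-AC".

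Under Data handling, the SAP shows that the raw material for adjustment is held. On the database: "This database will contain all project related data (demographic data, RSFC, ¹H-MRS and psychopathology data". On imaging: "MRI data (anatomic and rs-fMRI data) will be acquired". No analysis in the SAP gives the demographic or anatomic data a role. The supplied text describes neither the rs-fMRI preprocessing, nor the quantification of the metabolites, nor how controls are selected.

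**The concern.** Patients and healthy controls are formed by recruitment, not by allocation, so nothing in the design makes them alike. Any difference between them in age, sex, movement in the scanner or the grey-matter share of the spectroscopy voxel passes into the group effect of an ANOVA that does not account for it. What is at stake is the claim that borderline patients have abnormal connectivity or an abnormal glutamate/GABA balance at baseline. That claim could rest on older patients, more movement or a different tissue mix. Leaving the covariates open also allows them to be chosen after the results are seen.

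The second issue is smaller. The two halves of the sentence define the patient side differently, so two analysts could run different tests. The only patient groups named anywhere are ST-EF and ST-AC. If the RSFC test is a three-group omnibus by arm, it spends a degree of freedom on a difference between arms at baseline, before the arm-specific work has begun, and that difference says nothing about patients versus controls.

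**Working it through.** The plan gives no sample size, power, effect size or alpha, so there is no figure of its own to reproduce.

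**Inputs.** From the SAP: ANOVA, no stated covariate, two possible groupings. Assumed: two-sided alpha 0.05; n = 20 to 40 in each arm and n controls; both arms share one mean at T0; true difference d = 0.5 or 0.6 SD; patient-control covariate difference D = 0.5 to 0.8 SD; within-group correlation of covariate and outcome r = 0.3 to 0.4.

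**1. Confounding.** With no true difference, the spurious shift is b = D × r. It runs from 0.5 × 0.3 = 0.15 SD to 0.8 × 0.4 = 0.32 SD. For 2n patients against n controls, the noncentrality of the F test is λ = b² × (2n × n)/(3n) = b² × 2n/3.

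| n | b | λ | False-positive rate |
|---|---|---|---|
| 20 | 0.15 | 0.30 | 8% |
| 30 | 0.15 | 0.45 | 10% |
| 30 | 0.32 | 2.05 | 29% |
| 40 | 0.32 | 2.73 | 37% |

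The nominal rate is 5%. The rate rises with n because the shift is a bias and does not shrink as the sample grows. Weaker inputs do less harm: at 60 versus 30, a covariate explaining 5% of the variance (r² = 0.05) with D = 0.3 gives 6%.

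**2. Grouping.** With means (d, d, 0) the noncentrality is λ = d² × 2n/3 whether the arms are pooled or not; only the degrees of freedom differ. At n = 30 and d = 0.6, λ = 0.36 × 20 = 7.2.

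| Test (30/30/30, d = 0.6) | df | Power |
|---|---|---|
| Three-group omnibus | 2, 87 | 65.2% |
| Pooled patients vs controls | 1, 88 | 75.6% |
| Planned contrast (½, ½, −1) in the three-group model | 1, 87 | 75.6% |
| One arm vs controls | 1, 58 | 62.8% |
| One arm vs controls, Bonferroni for two | 1, 58 | 51.3% |

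Omnibus against pooled is 47% vs 58% at n = 20 and 79% vs 87% at n = 40. Across 20 to 40 per arm, controls equal to one or both arms, and d = 0.5 to 0.8, the omnibus loss runs from 0.2 to 11 percentage points.

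**3. Does adjustment raise power?** Take 60 patients and 30 controls, so N = 90 and h = 60 × 30/90 = 20. For one covariate, λ = d²h / [(1 − r²)(1 + hD²/(N − 2))]. At d = 0.5, d²h = 5, and unadjusted power is 60%.

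- Balanced covariate, r² = 0.2: λ = 5/0.8 = 6.25, power 70%.
- r = 0.4, D = 0.5: λ = 5/(0.84 × 1.057) = 5.63, power 65%.
- r = 0.3, D = 0.8: λ = 5/(0.91 × 1.145) = 4.80, power 58%.

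Under the imbalances that make confounding matter in step 1, adjusted power lies between 58% and 65%, against 60% unadjusted. The case for adjusting is therefore bias, not power.

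**The case against.** Four replies deserve weight.

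- **Correction may happen upstream.** Motion and tissue corrections can be made in preprocessing and quantification, and Data handling mentions processed data without describing the processing. A reader might infer that the plan makes no such correction; the documents support only that none is stated. Upstream correction would not deal with age or sex, and correcting each subject's series for movement does not by itself replace a group-level motion covariate.
- **Controls may be matched.** The supplied text has no eligibility or recruitment section, and the SAP refers to hypotheses set out elsewhere. If controls are matched on age and sex, that part of the concern largely falls away, though not the motion and tissue parts.
- **The plural may be loose wording.** A reader might infer that RSFC is split by arm. That is the likelier reading, but the baseline section never names the arms, and both the end of the same sentence and the next paragraph speak of patients and controls. Even if the arms are kept apart, lost power does not follow: it arises with an omnibus test or separate arm tests, not with a planned contrast, and the SAP specifies none of these.
- **The comparison is cross-sectional and partly exploratory.** It does not bear on which therapy works better. This limits the consequence but does not make an unadjusted group comparison safe to interpret.

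**Conclusion.** The concern stands in a limited form. The SAP names a method for a non-randomised comparison and states no covariates, and no matching rule appears in the supplied text, so a baseline difference in RSFC, Glx or GABA could be produced by age, sex, motion or tissue content. How large the bias would be cannot be derived from the documents; the 8% to 37% false-positive range illustrates the assumed inputs, and its upper end needs the least favourable value of each.

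The group wording needs reconciling whichever reading was meant. The ten-point power gap at 30 per group and d = 0.6 applies only if a three-group omnibus test was intended. A reader might also infer that adjustment will recover power; step 3 shows that it may or may not. The point should be acted on before the baseline data are analysed, but it does not touch the comparison of ST-EF with ST-AC.

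**What to change.** In the SAP's baseline section:

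1. Use one grouping for every MRI parameter and prespecify a single contrast of all patients against controls. It may be pooled or set as a planned contrast within a three-group model.
2. Estimate it by ANCOVA with age and sex, adding mean head motion for RSFC and voxel grey-matter fraction for Glx, GABA and their balance. Omit the tissue term if quantification already corrects for tissue, and say so.
3. State whether and how controls are matched.
4. Report the unadjusted ANOVA as a sensitivity analysis, so that readers see how far the result depends on the covariates.

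The demographic data and the anatomic and rs-fMRI scans are already to be collected, so the cost is SAP wording and deriving the motion and tissue summaries. Statistically, three covariates cost three residual degrees of freedom (88 to 85 at 60 versus 30), plus some precision where a covariate is unbalanced between the groups.

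### The SAP gives no between-arm estimate, confidence interval or test for any clinical outcome, only a per-patient Reliable Change Index within each arm

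*SAP*

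**What the plan says.** The SAP title sets the two therapies against each other: "Effects of emotion-focused vs. cognitive schema therapy interventions on emotion regulation deficits in borderline personality disorder". The heading of the follow-up section promises, for T0-T1, T1-T2 and T0-T2, an "analysis of treatment effects on primary and secondary outcome criteria".

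One paragraph follows, on changes of core symptoms and their clinical significance. It says "In each therapeutic condition the improvement of each patient in measures of the primary and secondary outcome criteria will be estimated", using the RCI, and gives this decision rule: "When the individual has a change score greater than 1.96 it can be assumed that the individual has improved". The next heading turns to MRI parameters.

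In that MRI section the arm contrast is explicit. A repeated-measures ANOVA will "test for effects of group belonging (ST-EF, ST-AC, and healthy subjects; ST-EF vs. ST-AC) on changes of RSFC, Glx and GABA over time", and a mixed model with treatment group as a factor is planned for the metabolite-connectivity associations.

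Clinical scores reappear only in the paragraph on the interrelation of clinical and neurobiological findings. There a mixed model takes the MRI measures that therapy affected significantly, together with "those clinical scores that reached the highest RCI. The detected significant interactions will be compared between the ST-EF and ST-AC treatment condition".

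The supplied protocol text is the table of therapy conditions. It labels ST-AC an active control and contains no statistical analysis.

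**The concern.** An RCI above the cut says that one patient's change is unlikely to be measurement error alone. It does not say why the patient changed. Both arms receive schema-based treatment and share the diagnostic phase and the amount of individual and group therapy. Within-arm improvement therefore mixes the emotion-focused component with shared treatment, natural course and regression to the mean. Only a comparison between arms can isolate that component, and the SAP does not specify one for symptoms.

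Any later statement that one therapy worked better would rest on an informal reading of two lists, or on an analysis chosen after the data were seen. With three intervals and several outcomes the choice would be wide, and no error rate would attach to it. If the comparison defaulted to RCI responder status, it would also discard information in the stored scores.

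**Working it through.** **1. What each planned analysis yields**

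| SAP analysis | Unit or target | ST-EF vs. ST-AC contrast? | Clinical score as outcome? |
|---|---|---|---|
| Baseline ANOVA and mixed model | MRI measures, patients vs. controls | No | No |
| RCI | Individual patient, within condition | No | Yes |
| Repeated-measures ANOVA | RSFC, Glx, GABA | Yes | No |
| Mixed model, metabolite-RSFC associations | Correlations between MRI measures | Yes | No |
| Mixed model, MRI and clinical scores | MRI-clinical interactions, selected inputs | Yes | No, an association |

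No row has a yes in both of the last two columns.

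**2. The only figure in the clinical section.** The two-sided 5% normal quantile is 1.95996, which gives the 1.96 cut. Under the RCI's normal-error model, a patient with no true change exceeds +1.96 with probability 0.025. That is a per-patient error rate. It gives no between-arm estimate, interval or trial-level error rate. The documents state no sample size, alpha, effect size, SD or reliability, so there is no design figure to reproduce. Everything below uses assumed inputs.

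**3. Reading the two RCI lists side by side.** Assume equal arms, a true proportion p reaching the cut, and n patients per arm. The probability of an observed difference of at least 10 points is exact binomial. The 95% chance range is ±1.96·√(2p(1−p)/n).

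| n per arm | p | P(difference ≥ 10 points) | 95% chance range |
|---|---|---|---|
| 30 | 0.25 | 0.45 | ±22 points |
| 30 | 0.35 | 0.50 | ±24 points |
| 30 | 0.50 | 0.52 | ±25 points |
| 50 | 0.25 | 0.30 | ±17 points |
| 50 | 0.35 | 0.35 | ±19 points |
| 50 | 0.50 | 0.37 | ±20 points |

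At n = 30, 10 points is exactly 3 patients. Counting only differences above 10 points lowers the n = 30 figures to 30-37%.

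**4. If responder status became the comparison by default.** Assume 30 per arm, pre-post correlation 0.5, reliability 0.80 and normal scores with equal SD. The RCI cut is 1.96·SD·√(2(1−0.80)) = 1.24 SD. The SD of change is √(2(1−0.5)) = 1 SD. With the reference arm improving 0.6 SD, P(Z > 1.24 − 0.6) = 26% respond. In the other arm 48% respond at an arm difference of 0.6 SD, and 37% at 0.3 SD. Simulated power (10,000 replicates per setting):

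| Reference improvement | Arm difference | RCI responders (chi-square) | t-test of change | ANCOVA |
|---|---|---|---|---|
| 0.6 SD | 0.6 SD | 43% | 63% | 75% |
| 0.6 SD | 0.3 SD | 15% | 21% | 26% |
| 0 | 0.6 SD | 33% | 62% | 74% |
| 0 | 0.3 SD | 11% | 21% | 26% |

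Repeat runs agree to within about 2 percentage points. Across all 48 settings examined (20, 30 or 50 per arm; correlation 0.5 or 0.7; reliability 0.80 or 0.90; the differences and improvements above) the order was ANCOVA, then t-test, then RCI. At 0.3 SD and 30 per arm, every method in the table is underpowered.

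**5. Precision of a baseline-adjusted estimate.** The 95% CI half-width in SD units is t·√(2(1−r²)/n), with 2n−3 degrees of freedom.
- r = 0.5: 0.45 at n = 30 and 0.34 at n = 50.
- r = 0.7: 0.37 at n = 30 and 0.28 at n = 50.

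**6. Therapy groups.** The protocol table gives group sessions of at most 10 patients. If a group of 10 belongs to one arm, variance is multiplied by 1 + 9·ICC. At an assumed ICC of 0.01 the half-width at n = 30 becomes 0.45·√1.09 = 0.47 SD. At 0.10 it becomes 0.45·√1.90 = 0.62 SD.

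**The case against.** The strongest counter-evidence is the interrelation paragraph, which does put clinical scores into a mixed model and does compare arms. The terms of the interactions are not defined, so reading them as brain-clinical associations is an inference. The paragraph's own heading supports that reading. Two arms can have the same association and different mean improvement, or the reverse. Even on a generous reading, only scores picked for the highest RCI enter, so the model cannot stand in for a comparison on the primary outcome.

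A second objection is scope. The supplied protocol is only a therapy table, and the hypotheses to which the SAP refers are not in the supplied text. The outcome criteria may be named elsewhere. This limits the finding to the documents supplied. But the SAP presents the tests it lists as those that address the hypotheses, and none compares arms on a clinical outcome.

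Third, the study is partly mechanistic: the full title goes on to associations with brain function and metabolism. That softens the emphasis, but the SAP has a separate heading for treatment effects on the clinical outcomes.

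Two technical points stand. The power figures support the choice of remedy and do not prove the omission. They also assume equal expected baselines, although the supplied text does not state random allocation, and independent patients despite group therapy.

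**Conclusion.** The concern holds and must be fixed. In the supplied documents, no between-arm estimate, confidence interval or test is specified for a clinical score as an outcome, although the title and the section heading call for one. This follows from the text and depends on none of the assumed numbers.

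The numbers show what is at stake. At 30 per arm, roughly half of trials with truly equal arms would show improved proportions at least 10 points apart, and about a third would do so at 50 per arm. These figures assume that 25-50% of patients reach the RCI cut and that patients are independent.

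**What to change.** Make the primary clinical analysis a between-arm comparison of the continuous primary score:
- Name the primary score in the SAP, and one primary time point, chosen by the sponsor in advance.
- Fit a linear mixed model with arm, visit (T1, T2), arm-by-visit and the T0 score as covariate. Report the ST-EF minus ST-AC difference with its 95% CI at the primary time point.
- Use the same model for the other time point and for the secondary outcomes.
- Add a therapy-group term, or a sensitivity analysis that allows for group clustering.
- Keep the RCI as supportive: proportion improved per arm, with the between-arm difference and its CI.

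Extending the repeated-measures ANOVA already planned for the MRI measures to the clinical scores would also supply a between-arm test. The baseline-adjusted model is preferred because ANCOVA had more power than a test of change in every setting examined.

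The cost is SAP wording and one model per outcome in SPSS, which is already the planned software. The clinical ratings "will be separately stored for the time points T0, T1 and T2", so no extra patients, visits or procedures are needed.

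### The SAP announces the clinical significance of symptom change, but its only visible patient-level rule, RCI > 1.96, establishes reliable change and ignores the end state

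*SAP*

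**What the plan says.** The SAP's follow-up analysis of treatment effects on the primary and secondary outcome criteria consists of one paragraph, titled "Evaluation of changes of core symptoms and their clinical significance". The paragraph does the following:

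- It applies a single tool to every patient in each arm. Improvement in "measures of the primary and secondary outcome criteria will be estimated by the Reliable Change Index (RCI").
- It says that the index carries norms: "The RCI provides information about the functioning of an individual before/after therapy on an outcome measure, including the normative information about this measure".
- It describes the calculation in the same sentence: "by dividing the difference between pre- and post-treatment scores by the standard error (that includes also the reliability coefficient" as well as the standard deviation of the measure).
- It explains the threshold: "The change will be considered as being unlikely the product of measurement error (i.e., considered reliable), if the RCI is greater than 1.96".
- It draws the patient-level conclusion from that threshold alone: "When the individual has a change score greater than 1.96 it can be assumed that the individual has improved". I read the change score here as the RCI.

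The RCI appears once more, in the SAP paragraph on clinical outcome parameters and neurobiological findings, where the model takes in "those clinical scores that reached the highest RCI". Neither the SAP nor the protocol text available (the table of therapy conditions) gives a cut-off between patient and normal range, a remission or recovery category, or a minimal important difference.

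**The concern.** The paragraph title makes two promises: to evaluate change, and to evaluate whether the change is clinically significant. The rule beneath it serves the first. A change larger than measurement error can still leave a patient severely ill, and nothing in the rule looks at the score after therapy.

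The stake is interpretation. This paragraph is the only analysis given for treatment effects on the clinical outcomes, so the share of patients classed as improved is likely to be a prominent clinical result. Reported under this title, it invites the reader to take reliable change as clinically significant change, which the rule cannot support.

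**Working it through.** **Inputs from the SAP.** The threshold is 1.96. The index is the pre-post difference divided by a standard error built from the SD and the reliability coefficient. The SAP gives no explicit formula, no reliability, no SD and no source for either.

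**Assumptions.** The standard error is that of a difference score, SD × sqrt(2(1 − r)). Reliability r runs from 0.70 to 0.95.

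**Step 1: the plan's own figure.** The two-sided 5% normal quantile is 1.95996, which rounds to 1.96. The threshold is therefore a test against measurement error, as the SAP itself says.

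**Step 2: what enters the index.** The inputs are the pre-post difference, the SD and r. The end score enters only through the difference. Two patients with equal change get equal RCIs wherever they finish. This step needs no assumption about r or severity.

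**Step 3: smallest change that passes.** In SD units this is 1.96 × sqrt(2(1 − r)):

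| r | sqrt(2(1 − r)) | Smallest passing change (SD) |
|---|---|---|
| 0.70 | 0.775 | 1.52 |
| 0.80 | 0.632 | 1.24 |
| 0.85 | 0.548 | 1.07 |
| 0.90 | 0.447 | 0.88 |
| 0.95 | 0.316 | 0.62 |

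A patient who starts at the patient mean and just passes ends 0.62 to 1.52 SD from it. That is inside a limit set 2 SD from the patient mean at every r shown.

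**Step 4: one end-state example.** Suppose the patient mean lies 3 SD above the healthy mean with equal SDs, so the midpoint cut-off is 1.5 SD. At r = 0.90, a patient who starts at the patient mean and just passes ends at 3 − 0.88 = 2.12 SD, on the patient side. With the same change, a patient who started below 1.5 + 0.88 = 2.38 SD ends on the healthy side. Both have the same RCI.

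The gap is not universal. At r = 0.70 the required change of 1.52 SD already exceeds the 1.5 SD from patient mean to midpoint, so a patient who starts at the mean and passes has crossed that cut-off.

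**Step 5: how large the gap could be.** This is a simulation of one million patients per setting, with baseline SD 1, r from 0.70 to 0.95, and true improvement with mean 0.5 to 1.5 SD and SD 0.5. All of these inputs are assumed.

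- Of those with RCI > 1.96, about 51% to 84% do not pass a cut-off 2 SD from the patient mean.
- About 17% to 51% do not pass a cut-off 1 SD from it.
- At r = 0.90 and mean improvement 0.8 SD, 45% are classed as improved. Of these, 77% fall short of the 2 SD cut-off and 41% short of the 1 SD cut-off.

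The spread shows that the size of the gap depends on inputs that the documents do not supply.

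**The case against.** The strongest case on the other side has five parts.

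- **The wording is modest.** The SAP says improved and never defines a success or a responder. For change beyond measurement error, improved is a fair word. This stands: a reader might infer that patients who remain ill are counted as treatment successes, but the SAP does not say so. What remains is that the classification sits under a title naming clinical significance.
- **The objectives are not visible.** Clinical significance appears only in a paragraph title. The hypotheses to which the SAP refers and the definitions of the outcome criteria are not in the available text, and an end-state definition could sit there. This also stands. A reader might infer that a stated trial objective goes unanswered, but the documents support only a title broader than the rule beneath it.
- **Norms may enter after all.** If the SD and reliability come from a normative sample, the phrase "including the normative information about this measure" has a plain meaning, so it cannot be called false. Norms used in that way still only scale the change. They do not locate the end score.
- **The numbers are illustrative.** The formula, the reliabilities and the 3 SD separation are assumptions. That a more reliable scale detects a smaller change is how the index is meant to work and is no defect in itself. This stands, but Step 2 needs none of these values.
- **The consequence is limited.** No visible hypothesis test uses the 1.96 classification, and the neurobiological model selects scores by highest RCI, not by the share improved. This stands: the damage is to the meaning of the clinical result, not to a test or to the MRI analyses.

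**Conclusion.** The concern holds as a mismatch between the paragraph title and the rule. In the documents available, RCI > 1.96 is the only patient-level criterion. It establishes reliable change, and a patient still in the patient range can meet it and be reported under clinical significance. This is more than a missing detail, because the stated rule cannot support the stated conclusion. The reliable-change half of the title is properly addressed.

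That conclusion rests on the SAP's description of the index alone. The smallest passing changes of 1.24, 0.88 and 0.62 SD at r = 0.80, 0.90 and 0.95 rest on the assumed difference-score formula and assumed reliabilities. A reader might infer from the simulation that most patients classed as improved in this trial will remain ill. The documents do not support that, since they give neither reliability nor baseline severity.

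**What to change.** 1. Label the RCI result reliable change, and require that it be in the improving direction for each scale.
2. State the source of the SD and the reliability coefficient for each scale, and say that normative information enters the RCI, if at all, only through these two quantities.
3. For each outcome scale with published norms, or with healthy-control scores if these are collected, define clinically significant change as reliable improvement plus a post-therapy score on the healthy side of a cut-off fixed before analysis.
4. Report both rates, reliable change and clinically significant change, by arm at T1 and T2.
5. For scales without a usable norm, report reliable change only and make no claim of clinical significance. If no scale has one, take clinical significance out of the paragraph title.

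The cost is SAP wording, a search for norms scale by scale, and one extra classification. Clinical ratings are already to be stored for T0, T1 and T2, so no new patient assessment is needed where published norms exist. The documents do not say whether healthy controls complete the clinical scales, so that source must be confirmed before it is relied on. The rate of clinically significant change will be lower than the rate from the RCI alone.
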